## Analysis methods

### Descriptive analyses

Baseline group differences will be explored with t-tests and  $\chi^2$ -tests.

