#### Primary analysis

The primary analysis will examine whether group CBTgrief is non-inferior to individual CBTgrief.

The analyses for primary and secondary outcomes will consist of multilevel, mixed linear models (MLMs) including time (pre-intervention, post-intervention, 3-month follow-up, and 6-month follow-up), group (Group CBTgrief vs. Individual CBTgrief), and their interaction (Time x Group). Two-level MLMs will be used to test the Time x Group interaction effect taking into account that symptoms are measured at several time points (level 1) that are nested within individuals (level 2).

We will report between and within-group effect sizes (Cohen's  $d$ ) for both group and individual-delivered CBTgrief to assess change in symptoms over time in the respective treatment groups.

The rationale for the non-inferiority limit: The choice of the non-inferiority margin of 0.5 SD was based on a clinical judgment, considering that the minimal important difference has yet not been established on PG-13. 0.5 SD corresponds to the border between a mild and medium effect, which very often corresponds to the border for a clinically meaningful effect (Norman et al., 2003) – also for stressor-related disorders such as PTSD (0.5-0.8 SD; Stefanovics et al., 2018). Moreover, a recent meta-analysis found that grief-focused CBTs delivered individually had a medium pooled effect on PGD symptoms with the lower bound of the 95% confidence interval (CI) of 0.49 (Hedge's  $g$  = 0.67, 95% CI: 0.49-0.85; Komischke-Konnerup et al., 2024). Importantly, RCTs investigating individual-delivered grief-focused CBTs that specifically included similar interventions and theoretical backgrounds as CBTgrief have found large effects on PGD symptoms compared to active and passive control groups (Cohen's  $d$  = 0.90 – 1.34; Boelen et al., 2007; Reitsma et al.,

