2023). Thus, based on previous research, individually delivered CBTgrief was expected to be highly effective in reducing PGD symptoms. Group CBTgrief may have potential advantages over individually delivered CBTgrief for an older bereaved population. In older bereaved individuals, loneliness and less social support are common, and a group format can offer a safe space and community for sharing one's grief experiences with and receiving support from other bereaved individuals. Furthermore, group-based treatment may be associated with more practical and financial advantages such as reduced costs and fewer specialized therapists needed to treat a larger group of individuals. Based on this rationale, a non-inferiority margin of 0.5 was chosen. This means that a mild effect up to the border of medium effect in favor of individual CBTgrief will be acceptable for determining the non-inferiority of group CBTgrief.

The true difference between group and individual delivered CBTgrief is assumed to be 0.0 and the one-sided significance level (alpha) of the test is 0.025 (Flight & Julius, 2016). A one-sided 97.5% CI interval approach will be used to test non-inferiority between group and individual CBTgrief. The 97.5% CI will be calculated for between-group differences at 6-month follow-up and post-intervention (Cohen's  $d$ ). The non-inferiority of group CBTgrief will be accepted if the lower bound of the 97.5% CI lies within the non-inferiority margin (Cohen's  $d = -0.5$ ). If the non-inferiority of group CBTgrief is accepted, we will further assess the potential superiority of group CBTgrief by close testing procedure (i.e., if the lower bound of the 97.5% CI lies above 0) (Flight & Julius, 2016).

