**Table 2.**

Descriptives and main effect results.

Measure	Group CBT			Individual CBT			Time x Group Interaction		
	n	Mean (SD)	Within group effect (Cohen's d )	n	Mean (SD)	Within group effect (Cohen's d )	F value	p value	Cohen's d (95% CI)
Primary outcome									
Prolonged grief symptoms (PG-13)									
Baseline									
Post-intervention									
3-month follow-up									
6-month follow-up									
Secondary outcomes									
Posttraumatic stress symptoms (PCL-5)									
Baseline									
Post-intervention									
3-month follow-up									
6-month follow-up									
Depressive symptoms (CESD-10)									
Baseline									
Post-intervention									
3-month follow-up									
6-month follow-up									
Anxiety symptoms (GAD-7)									
Baseline									
Post-intervention									
3-month follow-up									
6-month follow-up									
Loneliness (T-ILS)									
Baseline									
Post-intervention									
3-month follow-up									
6-month follow-up									
Social support (CSS)									
Baseline									
Post-intervention									
3-month follow-up									

6-month follow-up

Well-being (WHO-5)

Baseline

Post-intervention

3-month follow-up

6-month follow-up

Grief-related functional impairment (SDS)

Baseline

Post-intervention

3-month follow-up

6-month follow-up

Quality of life (SF-12)

Baseline

Post-intervention

3-month follow-up

6-month follow-up

---

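### The 6-month Cohen's d that decides non-inferiority is not tied to one contrast or one SD, and makes no adjustment for baseline PG-13

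*SAP*

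**What the plan says.** All the relevant text is in the SAP.

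- **Decision rule (Primary analysis).** "A one-sided 97.5% CI interval approach will be used to test non-inferiority between group and individual CBTgrief", and "The 97.5% CI will be calculated for between-group differences at 6-month follow-up and post-intervention", expressed as Cohen's d. Non-inferiority is accepted if the lower bound lies within d = -0.5.
- **Model (Primary analysis).** "Two-level MLMs will be used to test the Time x Group interaction effect". The fixed terms are time (pre-intervention, post-intervention, 3 and 6 months), group and their interaction. Between- and within-group d are described as measures of symptom change over time.
- **Margin (Primary analysis).** "The choice of the non-inferiority margin of 0.5 SD was based on a clinical judgment". No SD is named and no equivalent in PG-13 points is given.
- **Results shell (Table 2).** The only between-group d with a CI sits under "Time x Group Interaction", beside the F and p values. Raw means and SDs are listed by arm and visit.
- **Baseline (Descriptive analyses).** "Baseline group differences will be explored with t-tests and" chi-squared tests. Nothing links the result to the primary estimate.
- **Hypothesis (Primary hypothesis).** Non-inferiority is framed as reduction of PGD symptoms, assessed at six months.

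**The concern.** The primary verdict rests on one number, the lower confidence bound of a standardised difference. Three things determine that number, and the SAP leaves each open or makes weak use of it.

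1. **Contrast.** The decision rule points to a difference at 6 months. The model test and Table 2 point to a difference in change from baseline. The two point estimates differ by the chance baseline gap between arms, and their standard errors differ as well. The lower limit of Table 2's 95% CI is the same number as a one-sided 97.5% bound, so the table would print the deciding figure under the label of another contrast.
2. **SD.** A margin of half an SD has no fixed size in PG-13 points until the SD is named.
3. **Baseline.** Pre-treatment PG-13 enters only as one level of the time factor. The visit contrast ignores it and the change contrast subtracts it in full. Adjusting for it would generally give a narrower interval than either, and in a non-inferiority test the width of the interval helps decide the result.

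Concealing the arm codes until the analyses are done limits deliberate choice. It does not define the estimate or the margin.

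**Working it through.** **Inputs from the SAP.** Margin 0.5 SD; "The true difference between group and individual delivered CBTgrief is assumed to be 0.0"; "the one-sided significance level (alpha) of the test is 0.025"; 1:1 allocation. The one pair of figures that can be checked agrees: 1 - 0.975 = 0.025, z = 1.960, which is also the multiplier for a two-sided 95% CI.

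**Assumptions (not in the SAP).** Independent participants (clustering in therapy groups ignored); baseline SD 1; 6-month SD k = 1, 1.25 or 1.5; baseline to 6-month correlation r = 0.3, 0.5 or 0.7; 80% or 90% power for the visit difference, used only to obtain a plausible n.

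**n per arm.**
- 80%: 2(1.960 + 0.842)² / 0.5² = 62.8, so 63.
- 90%: 2(1.960 + 1.282)² / 0.5² = 84.1, so 85.

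**Variance of each contrast (times 2/n).** Visit: k². Change: 1 + k² - 2rk. Baseline-adjusted: k²(1 - r²).

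| k | Visit | Change, r = 0.3 / 0.5 / 0.7 | Adjusted, r = 0.3 / 0.5 / 0.7 |
|---|---|---|---|
| 1 | 1.000 | 1.400 / 1.000 / 0.600 | 0.910 / 0.750 / 0.510 |
| 1.25 | 1.563 | 1.813 / 1.313 / 0.813 | 1.422 / 1.172 / 0.797 |
| 1.5 | 2.250 | 2.350 / 1.750 / 1.150 | 2.048 / 1.688 / 1.148 |

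Adjustment cuts variance against the visit contrast by r² = 9 / 25 / 49%. Against change it cuts 35 / 25 / 15% (k = 1), 22 / 11 / 2% (k = 1.25) and 13 / 4 / 0.2% (k = 1.5).

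**How often visit and change give opposite verdicts** (bivariate normal estimates, true difference 0):

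| k, SD used for the margin | 63 per arm, r = 0.3 / 0.5 / 0.7 | 85 per arm, r = 0.3 / 0.5 / 0.7 |
|---|---|---|
| 1 | 26.6 / 22.5 / 20.0% | 19.1 / 13.2 / 10.0% |
| 1.25, baseline | 25.0 / 25.9 / 31.2% | 21.9 / 20.7 / 23.2% |
| 1.25, 6-month | 19.3 / 17.2 / 18.5% | 12.6 / 9.6 / 9.5% |
| 1.5, baseline | 21.3 / 24.0 / 32.3% | 21.0 / 22.9 / 30.1% |
| 1.5, 6-month | 15.2 / 14.8 / 17.9% | 9.4 / 8.3 / 9.3% |

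**Effect of the SD alone (visit contrast).** A margin of 0.5 six-month SDs equals 0.5 × 1.25 = 0.625 or 0.5 × 1.5 = 0.75 baseline SDs. The chance of declaring non-inferiority is:
- 63 per arm: 80.1% with the 6-month SD; with the baseline SD, 61.2% (k = 1.25) or 46.4% (k = 1.5).
- 85 per arm: 90.3% with the 6-month SD; with the baseline SD, 74.1% or 58.4%.

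If d were divided by the change-score SD (k = 1), the margin would be 0.5 × √(2(1 - r)) = 0.59 / 0.50 / 0.39 visit SDs.

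**Worked example.** 63 per arm, k = 1, r = 0.5, scores coded so that higher is better. The arms are equal at 6 months and the group arm is 0.20 SD better at baseline. The standard error of a visit difference is √(2/63) = 0.178, so a baseline gap larger than 0.20 SD in either direction arises by chance in 26% of trials.
- Visit: 0 - 1.960 × 0.178 = -0.349, passes.
- Change: -0.20 - 1.960 × 0.178 = -0.549, fails.
- Adjusted: -0.5 × 0.20 - 1.960 × 0.178 × √0.75 = -0.402, passes.

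**The case against.** **The decision rule is clear enough on its own.** An interaction test and a separate decision contrast can coexist, only the decision rule mentions the margin, and Table 2 is an unfilled shell with a row per visit. On this view the problem is mainly a label. Part of this stands: the visit reading is the more natural one for the rule itself. But the hypothesis, the description of d and the table header all lean towards change, and no sentence says how d is obtained from the model.

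**Baseline is not ignored.** If d is the interaction contrast, baseline is subtracted out. That is right. The lack of adjustment is complete only for the visit reading; for change, what is missing is a covariate or an equal-means constraint. Under randomisation both contrasts estimate the same treatment effect, so this is a loss of efficiency and not a bias. Against change the gain is negligible at high r and high k.

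**The SD may be stated elsewhere.** The SAP refers to the registry record for sample size and outcome details, and a d at a visit would conventionally use that visit's pooled SD. But the margin and the rule are written in the SAP, which names no SD.

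**The percentages are fragile.** This stands. At 150 per arm with equal SDs, opposite verdicts fall to about 1 to 5%. At k = 0.8 they run from 8 to 36% (63 per arm) and 2 to 29% (85 per arm), so the tables above are not full ranges. The baseline gap is also not the only cause: at 63 per arm and k = 1, power for change is 66% at r = 0.3 and 95% at r = 0.7, against 80% for the visit contrast. That net difference makes up more than half of the 26.6% and 20.0%.

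**Conclusion.** The concern holds. The SAP does not fix which contrast is compared with -0.5 or which SD scales both the contrast and the margin, and it makes less use of the baseline score than it could. The first two points follow from the text without any assumption. Their size depends on an assumed n, correlation and SD ratio, with independent participants and no true difference. For 6-month SDs of 1 to 1.5 times baseline, the two contrasts disagree in roughly 15 to 32% of trials at 63 per arm and 8 to 30% at 85. The choice of SD alone can move the chance of success at 63 per arm from 80% to 61% or 46%. A larger trial would show less. The baseline point concerns precision only, with a variance saving from 49% down to almost nothing depending on the comparison. The change should be made because it governs the primary verdict, but it does not invalidate the design.

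**What to change.** In the Primary analysis section:

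1. Define the primary estimate as the group versus individual contrast at 6 months from the mixed model with time as a categorical factor, adjusted for baseline PG-13 either as a covariate or by constraining baseline means to be equal across arms.
2. Take the one-sided 97.5% bound from that contrast.
3. Name one raw-score SD and use it for both the contrast and the margin. Do not use the model residual SD: with a random intercept it leaves out the variation between persons, so half of it is a smaller margin in PG-13 points. The choice between the baseline and the 6-month SD belongs to the sponsor and should be fixed before data access.
4. Label the d column of Table 2 as this contrast.

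The cost is SAP wording, one table label and model code. Pre-treatment and 6-month scores are already scheduled, so no new data are needed. The July 2024 SAP states that it was written before data access. If that has since changed, the amendment should give its date and say so.

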### **Secondary analysis**

The secondary analyses will follow the same principle as the primary analysis for PTSD, depression, anxiety, functional impairment, quality of life, treatment satisfaction, and well-being – testing for non-inferiority of group vs. individual CBTgrief.

For loneliness and social support, we will test the superiority of the group-based CBTgrief with MLMs using a two-sided alpha = 0.5 for significant differences, following our hypotheses.

Reliable changes in symptoms of PGD, PTSD, anxiety, and depression were computed by the Reliable Change Index (RCI; Jacobson & Truax, 1991) on the completer sample for both group and individually delivered CBT format and from pre- to post-intervention and 6-month follow-up.

Additionally, we will calculate the percentages of A) recovered participants (scoring above cut-offs before but below after treatment), B) unchanged participants (no change in terms of cut-offs before and after treatment), and C) deteriorated participants (scoring below cut-offs before treatment but above after treatment).

Based on the two-step criterion, individuals will be classified as 1) recovered (met both Cutoff A and RCI), 2) improved (met RCI but not Cutoff A), 3) unchanged (met none of the criteria), or 4) deteriorated (met RCI but symptom scores increased). See the procedure used by e.g., (Papa et al., 2013); Reitsma et al. (2023); (Treml et al., 2021).

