#### **Secondary hypotheses:**

- Group-based CBTgrief will show non-inferiority in reducing symptoms of PGD (PG-13) compared to individually delivered CBTgrief at post-intervention.
- Group-based CBTgrief will show non-inferiority in reducing symptoms of A) posttraumatic stress (PCL-5), B) depression (CESD-10), and C) anxiety (GAD-7) compared to individually delivered CBTgrief at 1) post-intervention and 2) six-month follow-up.
- Group-based CBTgrief will show greater reductions in loneliness (TILS) than individual CBTgrief at 1) post-intervention and 2) six-month follow-up.
- Group-based CBTgrief will show higher levels of received social support (CSS) than individual CBTgrief at 1) post-intervention and 2) six months follow-up.

Moreover, we will examine differences in terms of well-being (WHO-5), quality of life (SF-12), and grief-related functional impairment (SDS) between the two delivery formats.

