### **Additional analyses**

We will analyze the potential influence of treatment preference before randomization to treatment format and analyze potential differences in treatment satisfaction post-intervention.

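### Does non-inferiority testing of seven secondary outcomes need its own margins, or a shorter list of outcomes?

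*SAP*

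**What the plan says.** The SAP deals with these outcomes in four places.

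- **Secondary analysis** gives the rule: "The secondary analyses will follow the same principle as the primary analysis for PTSD, depression, anxiety, functional impairment, quality of life, treatment satisfaction" and well-being, the purpose being "testing for non-inferiority of group vs. individual CBTgrief". That makes seven outcomes. Loneliness and social support are handled separately, by a superiority test.
- **Secondary hypotheses** has a non-inferiority hypothesis for three of the seven: "Group-based CBTgrief will show non-inferiority in reducing symptoms of A) posttraumatic stress (PCL-5), B) depression (CESD-10), and C) anxiety (GAD-7"), at post-intervention and six months. After the list it adds that "we will examine differences in terms of well-being (WHO-5), quality of life (SF-12), and grief-related functional impairment (SDS") between the two formats.
- **Additional analyses** says the team will "analyze potential differences in treatment satisfaction post-intervention". Table 2 has no row for satisfaction.
- **Primary analysis** explains the margin. It was a clinical judgement, "considering that the minimal important difference has yet not been established on PG-13". The section then cites a general half-SD convention, a range of 0.5-0.8 SD for PTSD, and treatment effects on grief symptoms. "Based on this rationale, a non-inferiority margin of 0.5 was chosen". The rule is one-sided at 0.025: the lower 97.5% bound for d is compared with -0.5, and superiority is assessed next if non-inferiority is accepted.

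**The concern.** Two things look wrong on a first reading.

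First, four outcomes (functional impairment, quality of life, well-being, treatment satisfaction) seem to have two analyses: non-inferiority in one section and a comparison for differences in others. If both were live, the authors could report whichever looked better. With a modest sample, a moderately unfavourable result could be described as showing no significant difference when non-inferiority had not been shown.

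Second, the margin seems to be borrowed from another scale. The stated reason for relying on judgement is specific to PG-13. The treatment-effect evidence is specific to grief symptoms; the cited meta-analysis, for example, "had a medium pooled effect on PGD symptoms with the lower bound of the 95% confidence interval (CI) of 0.49". Among the seven outcomes only PTSD gets a figure of its own. The group format could then be called non-inferior on functioning or well-being against a margin that nobody had argued for on those scales.

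**Working it through.** The SAP gives no sample size or power (Sample size refers to the registry), so there is no stated figure to reproduce. The check is mainly a comparison of sections, followed by an illustration of size.

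**1. Which outcomes conflict**

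| Outcome | Secondary analysis | Elsewhere |
|---|---|---|
| PTSD, depression, anxiety | non-inferiority | non-inferiority hypothesis |
| Functional impairment, quality of life, well-being | non-inferiority | differences (Secondary hypotheses) |
| Treatment satisfaction | non-inferiority | differences, post-intervention (Additional analyses) |

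Seven outcomes are tested, three agree and four differ in wording. Comparisons touched: 3 outcomes × 2 time points + 1 = 7.

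**2. Is there a second decision rule?** Secondary hypotheses and Additional analyses name no test, alpha or criterion for the four outcomes. Where the SAP wants a superiority test, for loneliness and social support, it says so. Primary analysis itself uses the term between-group differences for the quantity whose interval decides non-inferiority, so the word does not imply a separate test. Secondary analysis holds the only operative rule.

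**3. Is the margin undefined?** Following the primary principle brings in the whole rule, including d = -0.5. The margin is standardised and needs no conversion between scales. Its direction is also settled: Primary analysis says the tolerated effect is one favouring individual therapy, so d is oriented with negative values favouring that arm, whichever way a scale is scored. The half-SD convention is presented as general, and the title of its source in References concerns health-related quality of life.

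**4. What the rule delivers.** The lower limit of a one-sided 97.5% interval equals the lower limit of a two-sided 95% interval, which is the interval shown in Table 2. One d with its interval gives the non-inferiority verdict (lower limit against -0.5), the superiority step (lower limit against 0) and a description of the difference.

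**5. How often could the two readings diverge?** Assume a two-sided 5% difference test, SE(d) = √(2/n per arm), a normal approximation, and no clustering, dropout or baseline adjustment. None of this, nor any n, is in the SAP. For a margin of 0.5, true difference 0 and one-sided 0.025:

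- 80% power: 2 × (1.96 + 0.842)² / 0.25 = 62.8, so 63 per arm.
- 90% power: 2 × (1.96 + 1.282)² / 0.25 = 84.1; the sample-size routine gives 85 per arm.

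The readings diverge when -1.96·SE < d < -0.5 + 1.96·SE.

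| n per arm | SE | Zone for d | Probability, true d = 0 | Probability, true d = -0.2 |
|---|---|---|---|---|
| 30 | 0.258 | -0.506 to +0.006 | 0.484 | 0.670 |
| 63 | 0.178 | -0.349 to -0.151 | 0.174 | 0.408 |
| 85 | 0.153 | -0.301 to -0.199 | 0.072 | 0.246 |

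The zone closes when 2 × 1.96 × SE = 0.5, that is n = 2 × (3.92/0.5)² = 122.9 per arm.

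Example at 63 per arm: d = -0.25 has a 95% interval of -0.60 to 0.10 and p = 0.16. The difference is not significant, and non-inferiority is not shown. Both statements are true of the same interval.

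**6. Would another margin matter?** At 63 per arm and true difference 0, power is 39% for a margin of 0.3, 61% for 0.4, 80% for 0.5 and 99% for 0.8. The value matters, but the SAP has fixed it at 0.5.

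**The case for a change.** The best case for a change rests on how Secondary hypotheses is built. It writes non-inferiority where it means it, writes directional superiority for loneliness and social support, and places WHO-5, SF-12 and SDS outside the list in different words. That looks deliberate. A non-inferiority verdict without a matching hypothesis, on a margin argued chiefly for grief symptoms, is weaker than one with both. Alignment would cost a few sentences.

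Part of this stands. The sections do not match, and the margin is not separately justified for depression, anxiety or the four outcomes in question. Treatment satisfaction also sits awkwardly: a measure planned only post-intervention does not fit a Time × Group model. An analyst would naturally use a plain between-group d at that time point, and its absence from Table 2, which is laid out for baseline and three later assessments, is unsurprising.

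The rest does not carry over into a change. Removing the four non-inferiority verdicts would let a general statement of aims override the specific analysis rule, a choice on which statisticians could reasonably differ. Restating -0.5 would only write down what is already inherited. The opening for selective reporting is narrow: there is one stated rule, the SAP commits to CONSORT reporting for non-inferiority trials, Table 2 shows the interval for all but satisfaction, and the arms are coded and concealed until all the non-inferiority analyses are done. Concealment limits the risk without removing it.

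**Conclusion.** No change is called for. This is an unevenness of wording between aims and methods on secondary outcomes, which an analyst resolves by following Secondary analysis as written: estimate d with its interval, compare the lower limit with -0.5, then with 0. Doing so also examines the difference, so the other sections are satisfied.

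At most seven secondary comparisons are involved, and the primary comparison on PG-13 is untouched. The divergence probabilities of 7% to 67% do not measure a defect in the plan, because they rest on an assumed difference test and assumed sample sizes of 30 to 85 per arm. The conclusion rests on two readings: that the same principle includes the standardised margin, and that a stated intention to examine differences, with no test attached, does not create a second decision rule. Both are the natural readings. Verdicts on these outcomes remain secondary and should be read alongside their intervals.

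### The superiority tests on loneliness and social support are set at a two-sided alpha of 0.5, so a true null is called significant half the time

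*SAP*

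**What the plan says.** The Secondary hypotheses section of the SAP makes two directional superiority claims, each at two time points. On loneliness: "Group-based CBTgrief will show greater reductions in loneliness (TILS) than individual CBTgrief at 1) post-intervention and 2) six-month follow-up". On social support: "Group-based CBTgrief will show higher levels of received social support (CSS) than individual CBTgrief at 1) post-intervention and 2) six months follow-up".

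The Secondary analysis section then gives the test: "For loneliness and social support, we will test the superiority of the group-based CBTgrief with MLMs", and continues "using a two-sided alpha = 0.5 for significant differences, following our hypotheses". The SAP states no other significance level for these two outcomes.

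The other error levels in the SAP are conventional. For non-inferiority, the Primary analysis section says "the one-sided significance level (alpha) of the test is 0.025". Its follow-on superiority claim is allowed only "if the lower bound of the 97.5% CI lies above 0". Table 2, which has rows for both loneliness and social support, reports Cohen's d with a 95% confidence interval.

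**The concern.** A two-sided alpha of 0.5 accepts a false positive in every second test of a true null. It agrees with no other error rate in the SAP. The same document also uses 0.5 for a different quantity ("a non-inferiority margin of 0.5 was chosen"), so a reader cannot take it for granted that the figure is a simple slip.

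These are the only outcomes with a stated hypothesis that the group format is better. The Primary analysis section also cites loneliness, lack of support and the community a group offers among its reasons for tolerating a margin of half a standard deviation. A significant result on either outcome would therefore be read as support for the group format, yet at this threshold it would carry almost no information.

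The rule also disagrees with the planned table. A result with |z| between 0.674 and 1.960 would be significant under the Secondary analysis section while its 95% interval in Table 2 includes zero. Under a true null this happens in 0.50 − 0.05 = 45% of tests.

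**Working it through.** **Inputs from the SAP**

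- Alpha 0.5, two-sided, for loneliness and social support (Secondary analysis).
- One-sided alpha 0.025 for non-inferiority, and a 97.5% lower bound above 0 for follow-on superiority (Primary analysis).
- 95% confidence intervals (Table 2).
- Two outcomes at two time points, so four stated hypotheses (Secondary hypotheses).

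**Assumptions, not in the SAP**

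- Correlations between the four test statistics: 0 to 0.7.
- Sample size: 20 to 100 per arm. The SAP leaves sample size to the registry record.

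**Step 1. What the stated level means.** The critical value is z(1 − 0.5/2) = z(0.75) = 0.674. The two-sided type I error is 2 × (1 − Φ(0.674)) = 0.50, which reproduces the stated alpha. One million simulated null z-statistics gave a rejection rate of 0.499. The share in favour of the group format is 1 − Φ(0.674) = 0.25.

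**Step 2. What the rest of the SAP implies.** One-sided 0.025 corresponds to two-sided 2 × 0.025 = 0.05, and a 95% interval corresponds to the same level. The critical value is z(0.975) = 1.960, with type I error 0.05 in total and 0.025 in favour of the group format. The stated level is 0.5/0.05 = 10 times as large, and its critical value is lower by a factor of 1.960/0.674 = 2.9.

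**Step 3. Several tests.** For k independent tests, the chance of at least one false positive is 1 − (1 − a)^k.

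| Tests | Direction | Alpha 0.5 | Alpha 0.05 |
|---|---|---|---|
| 2 | either | 1 − 0.5² = 0.75 | 1 − 0.95² = 0.098 |
| 2 | favouring group | 1 − 0.75² = 0.44 | 1 − 0.975² = 0.049 |
| 4 | either | 1 − 0.5⁴ = 0.94 | 1 − 0.95⁴ = 0.185 |
| 4 | favouring group | 1 − 0.75⁴ = 0.68 | 1 − 0.975⁴ = 0.096 |

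The real tests will be correlated. For four equally correlated normal statistics with correlation ρ, the chance of at least one false claim favouring the group format is 1 − ∫ φ(u) [Φ((c − √ρ·u)/√(1 − ρ))]⁴ du, where c is the critical value:

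| ρ | Alpha 0.5 | Alpha 0.05 |
|---|---|---|
| 0 | 0.684 | 0.096 |
| 0.3 | 0.586 | 0.087 |
| 0.5 | 0.521 | 0.078 |
| 0.7 | 0.451 | 0.065 |

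**Step 4. Size of effect that would pass.** For a simple two-group comparison with n per arm, the smallest significant standardised difference is about c × √(2/n):

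| n per arm (assumed) | Alpha 0.5 | Alpha 0.05 |
|---|---|---|
| 20 | 0.21 | 0.62 |
| 40 | 0.15 | 0.44 |
| 63 | 0.12 | 0.35 |
| 100 | 0.10 | 0.28 |

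This is only a guide, because the planned analysis is a repeated-measures mixed model. The ratio between the two columns is 2.9 whatever the sample size.

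**The case against.** The strongest reply is that this is a dropped zero and not a chosen error rate. Every other level in the SAP points to 0.05, Table 2 would show conventional intervals and p values to any reader, the outcomes are secondary, and the primary non-inferiority decision does not use this alpha. As to intent, that is very probably right. It does not remove the problem. The SAP exists to fix decision rules before data access, 0.05 is never stated for these tests, and a threshold corrected after the results are known is a post-hoc change.

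A second reply is that the number of tests is not settled. The hypotheses name two time points per outcome, but the Primary analysis section describes a Time x Group interaction, and Table 2 does not show whether there is one F test per outcome or one per time point. This stands in part. With one omnibus test per outcome there would be two tests, and the |z| cut-off, the 25% directional rate and the four-test figures would not apply as computed. The 50% per-test rate would be unchanged.

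Third, the correlations and sample sizes are not taken from the SAP. That is correct. They are illustrative, are shown as ranges, and the conclusion does not depend on them.

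**Conclusion.** The stated threshold is wrong as written. Under a two-sided alpha of 0.5, half of all true nulls on loneliness and social support would be declared significant, a quarter of them in favour of the group format; the level implied by the rest of the SAP gives 5% and 2.5%. The 50% figure follows from the definition of alpha and needs no assumption. The directional rate assumes a test with a sign, such as a contrast at one time point. The chance of at least one false claim for the group format (45% to 68%, against 6.5% to 10%) assumes four separate tests with correlations between 0.7 and 0. The primary non-inferiority conclusion is not affected. The error must be corrected, because it sits in the only decision rule the SAP gives for its two directional superiority hypotheses.

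**What to change.** In the Secondary analysis section, change the two-sided alpha for loneliness and social support from 0.5 to 0.05. This matches the one-sided 0.025 in the Primary analysis section and the 95% intervals in Table 2. Issue it as a dated correction to the SAP before the concealed treatment codes are revealed, so that it cannot be read as a response to the results.

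A Holm adjustment across the four outcome-by-time tests could be added, but that is a separate choice about multiplicity and the correction does not depend on it.

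The cost is one changed number. No new data, change of design or clinical decision is needed.
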